8.1. General

MASS2 will use the MATS Research System for the same purposes of MASS. Components of the MATS Research System are detailed in Table 1.

Table 1- MATS Research System components

Model Number	Component (Manufacturer)		Investigational or Commercially available
MC1VR01	Micra™ Implantable Device (Medtronic)		Commercially available in Europe
2090	Medtronic Carelink Programmer (Medtronic)		Commercially available in Europe
SW022	Micra™ Software Version 1.1 (Medtronic)		Commercially available in Europe
No model number	MATS Software Version 1.0 (Medtronic)		Investigational
ER220	Extended Range Holter Monitor System (Medtronic)	DR220 Holter (Medtronic)	Commercially available in Europe
		ERX10 Extended range Tel-B antenna cable (Medtronic)	Investigational

In addition to the MATS Research System, the MASS2 study will use the echocardiography equipment available at the hospital to conduct echo examination.

Instructions for intended use, including indications and contraindications of the components of the MATS Research System used in this study, as well as medical procedures and information regarding material in contact with tissues or body fluids are provided in their respective manuals and instructions for use.

8.1.1. Micra Implantable Device

The Micra Implantable Device (MC1VR01) is a miniaturized, single chamber pacemaker that provides bipolar sensing and pacing in the right ventricle. The device has an activity sensor that detects the subject's body and heart movement.

The Micra Implantable Device is commercially available in Europe and will be used according to the approved and intended use in the MASS2 study.

8.1.2. Medtronic Carelink Programmer (2090) and Micra Software (SW022)

The Medtronic Carelink Programmer (2090) and Micra Software (SW022) Version1.1 are used to communicate with the Micra device. The use of a programmer head, Medtronic Model 2067 or Model 2067L, based on standard telemetry B, is required for communication between the Micra device and the Medtronic Carelink Programmer.

This document is electronically controlled. Printed copies are considered uncontrolled.

Confidential

The Medtronic Carelink Programmer (2090) and Micra Software (SW022) Version1.1 are both commercially available in Europe and will be used according to the approved and intended use in the study.

8.1.3. MATS Software

The Investigational MATS software Version 1.0, created by Medtronic, will be downloaded into the Micra device using the Medtronic Carelink Programmer to enable the telemetry transmission of accelerometer data from the Micra device to the Extended Range Holter Monitor System. The MATS software can be manually removed from the Micra device using the Medtronic Carelink Programmer. In case the software is not manually removed, it automatically deactivates after 48 hours.

To use the MATS Investigational Software with a Medtronic Carelink Programmer, the software must be first installed on the programmer through the Medtronic Software Distribution Network (SDN). When the investigational MATS software is installed on the Medtronic Programmer, the installed Medtronic Programmer will be labeled to indicate that it contains investigational software. The installation only needs to be done once per programmer.

At the beginning of each MASS2 session, the MATS software needs to be activated the programmer, selecting the "MATS Rev 1.0 - For Investigational Use Only" from the list displayed. After the MATS software is activated, an access code is required to communicate with the Micra device. This access code is unique for each device serial number and will be provided by the Study Team.

When the MASS2 study is complete, the software should be uninstalled from the programmers on which it was installed using the Medtronic SDN. Instructions on how to install/uninstall the MATS software on/from the programmer and on/from the Micra device are described in the MATS User Manual (DSN018088 Version 2.0 Initial Release).

8.1.4. Extended Range Holter Monitor System

All subjects in this study will use a customized investigational Extended Range Holter Monitor System (ER220). This ER220 system uses a commercially available Holter (DR220) and an investigational extended range telemetry-B antenna (ERX10) created by Medtronic. The ERX10 antenna is based on a market-released cable that communicates with implanted devices via telemetry; it has been modified to extend its range and increase noise rejection in order to communicate with the Micra device inside the heart.

8.2. Manufacturer

Each of the MATS Research System components is manufactured by Medtronic.

8.3. Packaging

When the investigational MATS software is installed on the Medtronic Programmer, the loaded Medtronic Programmer will be labeled to indicate that it contains investigational software.

The Investigational Holter will be labeled according to the local regulatory requirements.

8.4. Intended Population

The target population will consist of subjects aged ≥ 18 and implanted with a Micra device and not in Atrial Fibrillation (AF).

This document is electronically controlled. Printed copies are considered uncontrolled.

Confidential

8.5. Equipment

In case of technical support and maintenance or calibration of study-specific equipment, the Investigators can contact the appropriate Medtronic study personnel. Medtronic Study Contact list will be provided under a separate cover.

8.6. Product Use

Principles of operation of the Investigational MATS software and ERX10 Extended range Tel-B antenna cable will be provided in the MATS User manual (DSN018088 Version 2.0 Initial Release) and ERX10 Instruction Sheet (DSN011766 Version 2.0 Initial Release), respectively.

8.7. Product Training Requirements

Training on the MATS Research System is required prior to the clinical site's first subject procedure.

8.8. Product Receipt and Tracking

Date when the site receives the installation of the MATS software from the Medtronic SDN will be maintained during and after the clinical investigation. Each programmer loaded with the MATS software will be traced with the programmer serial number.

Date when the site receives the Holters will be maintained during and after the clinical investigation. Each received Holter will be traced with the Holter serial number.

8.9. Product Storage

To use the MATS software installed on the programmer, the software must be first activated. Furthermore, a unique access code is required to communicate with each patient's device serial number. Therefore, the programmer installed with the MATS software can also be used outside the study purposes and there are no storage requirements.

Storage area of ER220 Holters should be locked/secure with access limited only to approved study staff.

8.10. Product Return

The investigational MATS software will be removed from the installed programmers only at the end of the clinical study via the Medtronic SDN.

Holters will be shipped back to Medtronic at the end of the clinical study.

8.11. Product Accountability

Product accountability will be documented in the electronic Case Report Forms (e-CRFs) which will be maintained in the Electronic Data Capture (EDC) system.

The e-CRF will track at least: date of receipt / installation of the investigational product / software from the site, serial number of the product, location of the product, date and reason for return / uninstallation of the product / software.

This document is electronically controlled. Printed copies are considered uncontrolled.

Confidential

9. Selection of Subjects

9.1. Study Population

The target population will consist of subjects aged ≥ 18 , implanted with a Micra device and not in AF.

9.2. Subject Enrollment

The subject will be considered enrolled after both the Investigator and the subject have dated and signed the Informed Consent Form (ICF).

9.3. Inclusion Criteria

- Subject is ≥ 18 years old
- Subject is implanted with a Micra device
- Subject or witness (if applicable as per local regulation) is able and willing to provide Informed Consent

9.4. Exclusion Criteria

- Subject is in atrial fibrillation
- Subject is not able to perform study requirements

10. Study preparation

10.1. Investigator/Investigation site selection

An investigator/investigation site may be included in the investigation if the investigator/investigation site complies with the following requirements:

- Investigator/site is qualified by training, education, and relevant experience appropriate to the use of the product and associated procedures
- Investigator/site expects to have adequate time and resources to conduct the study throughout the duration of the study
- Investigator/site has access to an adequate number of eligible subjects
- Ability to comply with applicable Ethics Committee (EC) and regulatory requirements
- Investigator is not debarred, disqualified, or working under sanctions in applicable regions
- Investigation site has an echo machine available to conduct the echo recording

Qualification visits will be waived for the MASS2 study, since the assessment of the investigator or site will be conducted based on previous experience in conducting clinical studies for Medtronic and more recent visits for similar therapeutic areas.

10.2. Site activation

Before performing study related activities, all requirements shall be fulfilled, including, but not limited to the following:

- EC approval (and voting list, as required by local law) of the current version of the Clinical Investigation Plan (CIP) and ICF.
- Regulatory authority approval or notification (as required per local law)
- Fully executed Clinical Trial Agreement (CTA)
- Curriculum Vitae (CV) of investigators and key members of the investigation site team (as required by local law).
- Documentation of delegated tasks
- Documentation of study training.

Additional requirements imposed by the EC and regulatory authority shall be followed, as appropriate.

Medtronic may distribute pre-populated study-specific Investigator Site File (ISF) and will provide site with documentation of study center/investigator readiness. Evidence of center/investigator readiness must be received prior to subject enrollment and must be filed in the ISF.

11. Study Procedures

Subject may be at the hospital specifically for the MASS2 or for other reasons independent from MASS2, such as routine clinical care. Subject will undergo following study procedures:

- **Informed consent procedure** - The subject will be screened to verify eligibility criteria and willingness to participate to the study. After both subject and investigator sign and date the ICF, the subject is considered enrolled.
- **Baseline, Medical History** – Collect Baseline and Medical History information
- **Micra Implant Procedure History** – Collect information on the previous Micra implant procedure
- **MATS software download** - After subject enrollment, the investigational MATS software will be downloaded into the implanted Micra device.
- **Holter examination** - The subject will be equipped with the investigational ER220 Holter and Holter telemetry will be turned ON. The duration of transmission of Holter telemetry data is recommended to be set at 4 hours and should not exceed 24 hours. The subject will be requested to perform a posture and exercise test. The test consists of a repetition of postures and exercises for each of the three rate response activity vectors (V1, V2 and V3), such as:
 - If the subject is not being paced, temporary overdrive pacing at approximately 10 bpm above the intrinsic heart rate for 30 seconds
 - Supine, right recumbent and left recumbent postures for 1 minute each
 - Sitting and standing for 1 minute each
 - Walking at a normal pace for 2-3 minutes

This document is electronically controlled. Printed copies are considered uncontrolled.

Confidential

Subject is allowed to have recovery time during the test as needed. If no recovery is needed, it is possible to move to the next exercise as soon as the subject is ready. In case part of the test cannot be completed, this should not be considered a deviation.

The Holter will allow recording of ECG and accelerometer data during the posture and exercise test, for each of the three rate response activity vectors.

- **Echo examination** - After the posture and exercise test is completed, subject will undergo the echo recording: 4 chamber, left atrial volume, left ventricular outflow track (LVOT) velocity time integral (VTI), pulmonic valve VTI, mitral flow, tricuspid flow. During echo recording, accelerometer data will continue to be recorded on the ER220 Holter. In case the Holter electrodes complicate the echo examination, the electrodes can be moved. After the echo recording, Holter will be removed and Holter telemetry will be set OFF.
- **MATS software removal** - After the echo examination, the Holter will be removed from the subject and the MATS software will be manually removed from the implanted Micra device, using the programmer.
- **Subject exit** – After removal of MATS software, subject will be exited. (Note: in case the MATS software was not manually removed, the subject will be exited after the automatic deactivation of the software).

11.1. Role of the sponsor representatives

Sponsor representatives may provide support as required for the study under supervision of the Principal Investigator, including:

- Study training relevant and pertinent to the involvement of personnel conducting study activities and investigator responsibilities
- Technical support in installing/uninstalling the MATS software into/from the Programmer via the SDN
- Technical support in downloading/removing the MASS2 into/from the implanted Micra device, under the supervision of a study investigator
- Monitoring and auditing activities

No data entry, shall be performed by Medtronic personnel or their representatives at sites

11.2. Schedule of Events

List of study procedures and study events/tests is reported in Table 2. Study procedures will occur all on the same day.

Table 2 – Procedure and events/tests in MASS2

Procedure	Events/Tests
Informed Consent procedure	1. Inclusion/exclusion assessment
	2. Informed Consent Form signature
Baseline, Medical History	3. Collect information on Baseline, Medical History

This document is electronically controlled. Printed copies are considered uncontrolled.

Confidential

Procedure	Events/Tests
Micra Implant Procedure History	4. Collect information on the previous Micra implant procedure
MATS software download	5. Initial Device interrogation
	6. MATS software downloaded into Micra device
Holter examination	7. Holter attached and Holter telemetry set to 4 hours
	8. Holter recording during posture and exercise test: V1, V2, V3
Echo examination	9. Echo recording: Use the permanently programmed, chronic vector
	10. Holter removed and Holter telemetry set to OFF
MATS software removed	11. MATS software removed from Micra device
	12. Final Device interrogation
Subject exit	13. Subject exited

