11.8. Recording Data

Subject data and product accountability data will be collected on the e-CRFs and will be reported to Medtronic via the RDC System, Oracle Clinical.

Device interrogation data will be saved on supported media and will be delivered either electronically via a secure web-based application (Clinical Transfer or BOX) or via mail. Device data are recommended and not mandatory. Missing device interrogation data should not be considered as deviation.

ECG and accelerometer data will be saved on the Holter flashcard and will be delivered either electronically via a secure web-based application (Clinical Transfer or BOX) or via mail.

Echo data will be saved on supported media and will be delivered either electronically via a secure web-based application (Clinical Transfer or BOX) or via mail.

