enrollment until the problem is resolved or ultimately terminating the investigator's participation in the study.

Examples of MASS2 deviations include but are not limited to:

- 1 Failure to obtain subject IC
- 2 Inclusion/exclusion criteria not met
- 3 Missing ECG /accelerometer/echo data

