
Improper MATS software download and manual removal:
 
Download and manual removal of the MATS software from the Micra device, if done improperly may impact implanted device functionality.
	
 Access codes, software version, and software limitation requirements (no other software present in the device RAM) are in place for MATS software download Programmer user is informed of presence of MATS investigational software on the Micra device on user interface If the download of the MATS software does not execute correctly, this will be detected by the Micra device and the software will not be activated The MATS software can be manually removed from the Micra device. The MATS software has an internal timer that automatically deactivates the software 48 hours after download

Interactions of the MATS software with existing Micra device features:
 
MATS software runs from the device RAM and sends the accelerometer and temperature sensor data via telemetry to the ER220 Holter, potentially causing an unintended interaction.
	
 Potential Micra device interactions with the MATS software running with existing Micra device were analyzed. Interactions were limited to the use of telemetry for sensor data uplink and rate response, which were identified to be low risk as no direct therapeutic functionality would be affected. Verification activities will be performed to ensure no related negative interactions

Missing/ misleading information causing insufficient/ inappropriate medical intervention:
 
Errors, omissions, or ambiguities in diagnostic data collected/ presented to the user, or corruption of software that influences the user's ability to make an informed medical decision.
	
 Misleading information is prevented because MATS temperature sensor data is not viewable by study center personnel and any data not used for diagnosis purposes Data integrity is controlled via ECC memory checks in the Micra device Information on MATS supplemental markers on real-time EGM will be provided in training and User Manual User Manual will instruct investigator to program optimum accelerometer vector in subject' Micra devices prior to leaving the study

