12.2. Potential Benefits

The MASS2 may offer no benefit. It is possible that improved rate response settings may be programmed as a result of the test. Improved rate response may provide improvements for optimal pacing rate.

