17.1. Monitoring

It is the responsibility of Medtronic to ensure proper monitoring of the study per regulations. Appropriately trained Medtronic personnel or delegates appointed by Medtronic will perform study monitoring at the study center in order to ensure that the study is conducted in accordance with the CIP, the CTA, and applicable regulatory requirements. Medtronic must therefore be allowed to access to the subject's clinic and hospital records when so requested as per the ICF and CTA. Procedures in the CIP require source documentation, which will be maintained at the site. Source documents, which may include subject medical records, device interrogation files, must be created and maintained by the investigational site team. Data which will be directly collected in the e-CRF will not be considered source document, unless there is no other source document and it is authorized by the study-specific monitoring plan for that specific data. Worksheet may be used and will not be considered source document. The investigator will clearly mark clinical record to indicate that the subject is enrolled in this clinical investigation. Where copies of the original source document as well as print outs of original electronic source documents are retained, these shall be signed and dated by a member of the investigation site team with a statement that it is a true reproduction of the original source document. One-hundred percent of ICF will be monitored for this study. More details on monitoring will be documented in the Monitoring Plan.

The principal investigator(s) and his/her delegate(s) shall be accessible to Medtronic field personnel and the Clinical Study Manager. This accessibility is of particular importance for reviewing data in the e-CRF. Direct access to patient medical files for source data verification (if applicable) will need to be granted and prepared prior to any monitoring visits.

A list of participating Investigators and sites and list of Monitors will be provided to the sites on a separate cover.

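### Does the plan leave open which accelerometer vector is in use during the echo recording?

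*Combined protocol and SAP*

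**What the plan says.** Section 11 describes the Holter examination: "The test consists of a repetition of postures and exercises for each of the three rate response activity vectors (V1, V2 and V3"). Table 2 lists this as step 8. Step 9 follows: "Echo recording: Use the permanently programmed, chronic vector". This is the only use of the phrase, and the description of the echo examination in Section 11 names no vector.

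Programming is mentioned in two other places. A risk-minimization entry in Table 3 (Section 12.1) says the "User Manual will instruct investigator to program optimum accelerometer vector in subject" devices, with the deadline given as "Micra devices prior to leaving the study". Section 12.2, on potential benefits, adds: "It is possible that improved rate response settings may be programmed as a result of the test". None of the 13 steps of Table 2 is a programming step.

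On records, Table 2 schedules device interrogations at steps 5 and 12. Section 11.8 says of these files: "Device data are recommended and not mandatory. Missing device interrogation data should not be considered as deviation". Section 11.9 gives "Missing ECG /accelerometer/echo data" as an example of a deviation and does not mention the vector. Section 17.1 says: "Procedures in the CIP require source documentation, which will be maintained at the site". It goes on to give interrogation files as an example of source documents.

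**The concern.** The primary objective (Section 6.1) uses echo to explain what the accelerometer senses. Echo is the procedure that MASS2 adds to its predecessor, and under step 9 each subject has echo in a single vector. An analyst therefore needs to know which vector that was.

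The plan appears to leave this open in two ways.

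- **Which vector.** Programming that results from the test must fall after step 8, and Table 3 requires it before exit. Echo lies inside that interval. A vector set just after the test could be called permanently programmed, so one site might record echo in the pre-visit vector and another in a newly set one, each believing that it had followed step 9.
- **Which record.** The two interrogations stand on either side of echo and their files are optional. If they showed different vectors, the pair alone would not say which applied at step 9.

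With approximately four centers, the echo segments might then be impossible to sort by vector. They could still be described, but with less detail.

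**Working it through.** The plan states no figure on this point, so the check sets the passages side by side. No view is taken on which vector should be programmed, or when.

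**1. Meaning of step 9.** The step gives two conditions: the vector is permanently programmed, and it is chronic. The pre-visit vector meets both. A vector set minutes earlier, after a same-day test, can meet the first but hardly the second. Read whole, the phrase identifies the pre-visit vector, whatever the order of later programming.

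**2. Do Table 3 and step 9 conflict?**

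| Place | What it fixes | What it leaves open |
|---|---|---|
| Table 2, step 9 | The vector for echo | Any later programming |
| Table 3 | A deadline: before leaving the study | Position relative to echo |
| Section 12.2 | Nothing; it describes a possibility and speaks of settings, not of a vector | Everything |

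At least one sequence satisfies every row: echo in the chronic vector, then any programming, then exit. The passages are compatible, so there is no contradiction to reconcile.

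**3. What the interrogations can show.** There are three possible vectors at step 5 and three at step 12, so 3 × 3 = 9 possible pairs. These are cases, not probabilities.

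- If *chronic* means the pre-visit vector, the step 5 file gives the intended echo vector in all 9 cases.
- If *chronic* is disregarded, the pair settles the matter only when the two files agree, in 3 cases. The other 9 − 3 = 6 leave two candidates.

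The apparent ambiguity therefore depends entirely on setting one word of step 9 aside. The counts say nothing about how often a difference would occur.

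**4. Where vector detail is kept.** The plan does not list e-CRF fields for the clinical procedures. It also gives no order or label field for V1, V2 and V3 in step 8, although Section 11 expects Holter data for each of them. Table 4 (Section 12.1) refers to detailed instructions in the study worksheets, and Section 8.1.3 sends software operation to the User Manual. Vector labelling thus appears to be handled below the level of the plan throughout, so the absence of a named field for echo says little about whether the vector is recorded.

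**5. Effect on the result.** Section 6.1 sets no endpoints. Section 15 plans no hypothesis test and already promises the number of subjects in each analysis. No estimate, error rate or sample size in the plan depends on this point.

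**The case for a change.** The strongest case for a change is that the plan treats the vector as material: it repeats the test per vector and specifies one for echo. A setting that matters enough to specify should be recorded. The step 5 file, even if sent, shows the setting before the test moved through three vectors. It shows the intended echo vector and does not verify the one in use. If a device stayed in a test vector by mistake, two agreeing interrogations would not reveal it. Worksheets may be used but are not source documents under Section 17.1. Description is the whole objective, so a descriptive loss is not trivial, and a field costs almost nothing.

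Much of this is true. The term is undefined, the programming has no place in Table 2, and no required record of the echo vector is named. What does not follow is that the plan is wrong. A device left in a test vector is a departure from step 9 and not a consequence of its wording. The optional status in Section 11.8 appears in a section on saving and delivering data to the sponsor. Both interrogations remain scheduled steps, and Section 17.1 requires source documents to be kept at the site, with interrogation files as one possible form; that wording helps but guarantees nothing. Nothing in the documents suggests that sites would order the steps differently, and study and system training are required before the first procedure (Sections 8.7 and 10.2).

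**Conclusion.** No change to the plan follows. A site that follows step 9 as written records echo in the subject's chronic vector, and the descriptive account stays sound. No stated rule or figure is shown to be wrong. A definition, a step order or a field name would only write down what step 9 already implies or what the supporting documents may already contain.

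The size is small: a point of traceability in an exploratory study, without effect on any inference. The documents give no share of datasets that might be unclear, and quoting the whole range from none to all of the approximately 40 would not be an estimate.

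The conclusion rests on two assumptions. The first is that *chronic* has its ordinary meaning, the setting in place before the visit. The second is that vector labels for step 8 and step 9 are kept in the e-CRF, worksheets or Holter file. The second cannot be confirmed from the plan. If it failed, echo segments could still be described, with the intended vector taken from step 9 and the step 5 interrogation where that file is available.
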